WHO	World Health Organization

PROTOCOL SUMMARY

Title:	Family Intervention With Caregivers Of Children With Dental Needs
Précis:	The study is a multi-site, double blind, parallel arm, community-based randomized controlled trial (phase III RCT) to evaluate the effectiveness of new referral approaches to increase receipt of dental care among inner-city urban and rural elementary school children who were screened at school and have restorative treatment needs. The study has 5 arms: The experimental intervention is the use of a theoretically driven CSM referral letter alone, the CSM letter plus a Dental Information Guide, a reduced CSM referral letter alone, or a reduced CSM referral letter plus a reduced Dental Information Guide. The control strategy is the use of a modified standard referral letter. All RCT participating K-4 grade children will receive a screening at the beginning of the school year and at the study end point 7 months later to determine if the child received dental care.
Objective	
Primary: To evaluate the effectiveness of experimental (new) versus standard referral approaches given to parents/caregivers in increasing receipt of dental care among their children in grades K-4.
 
Secondary: To assess changes in parent/caregiver illness representation/perception and behavioral intention between enrollment (beginning of school year), 2-week and 7-month follow-up (end of school year) to understand the underlying mechanisms of the new vs. standard referral approach that result in receipt of dental care.

Population:	Population information: sample size=660 caregivers to be randomized; children will be both male and female, grades K-4; inner city African Americans (Bedford and E Cleveland, OH) and rural Whites and Hispanics (Cowlitz and Lewis counties, Washington State).
Phase:	III
Number of Sites:	
(1) East Cleveland City School District (ECCSD, Cleveland, OH), and Bedford City School District (BCSD, Bedford, OH).
 
(2) Cowlitz County (CCSD, WA), and Lewis County (LCSD, WA).

Description of Intervention:	The experimental intervention is the use of a theoretically driven CSM referral letter alone or the letter plus a dental information guide. The control strategy is the use of a modified standard referral letter.
Study Duration:	10 months
Subject Participation Duration:	1 year

Estimated Time to Complete Enrollment: 3 months

SCHEMATIC OF STUDY DESIGN

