3.2.2 Secondary Outcome Measures

The first secondary outcome (mediator) will be change in the overall Illness Perception Questionnaire-Revised for Dental (IPQ-RD), cognitive (identity, consequences, timeline, cause, cure/controllability) representation subscale scores (Weinman et al. 1996; Barrowclough & Lobban 2001; Moss-Morris et al. 2002; Bonetti et al. 2010).

The other secondary outcome (mediator) will be a change in behavioral intention (Luzzi & Spencer, 2008; Ajzen, 1991, 2002). Behavioral intention will be assessed using a caregiver questionnaire and is measured by the summative score of 2 items (e.g., “I want to take my child to the dentist”, and “I plan to take my child to the dentist” on a 5 point scale (Luzzi & Spencer, 2008). The use of these measures will allow us to better understand the mechanisms of action of the intervention based on

our conceptual model. The change in IPQ-RD and behavioral intention scores will be calculated between baseline, two week, and final follow-up. A decrease in IPQ-RD scores (i.e. lower score) indicates better illness representation/perception, while increase in behavioral intention scores indicate a higher intention to take the child to dentist for follow-up care.

Table 3.2.1 Summary of measures, timeline, and source

Variable Type	Measure	Timeline ¹	Source
Exposure (Intervention Study Arms)	
 • CSM referral letter alone • CSM referral letter + DIG • Reduced CSM referral letter alone • Reduced CSM referral letter + DIG • Modified Standard letter 	At randomization	Mosleh et al. 2009 Ohio Department of Health Bureau 2007
Primary Outcome	Dental exams 
 • Child's receipt of dental care 	Beginning and end of school year	ICDAS (Pitts 2004)
Secondary Outcomes (Mediators)	IPQ-RD 
 • Caregiver illness perception Caregiver Questionnaire 
 • Behavioral intention 	Baseline, Two-week, and Exit	Barrowclough et al. 2001 Ajzen 2002; Conner & Armitage 1998
Moderators	Caregiver Questionnaire 
 • Caregiver literacy • Caregiver self-efficacy² • Caregiver dental fear • Caregiver perceived stress • Subjective norm² • Dental insurance status Site (urban/rural)	Baseline	Bennett et al. 2003 Finlayson et al. 2005 Humphris et al. 1995 Cohen & Williamson 1988 NHANES IV Ohio, Washington

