Confounders	Child's age, race, dental visit Caregiver socio-demographics (age, race, SES, education, marital status)	Baseline	NHANES IV
Subject compliance with Intervention	
 • Whether the referral letter (and DIG) was received (generic code) • Whether the referral letter (and DIG) was read/understood (Postcard) 	Within 2 days after Baseline dental exam	

1. **Baseline:** prior to screening dental exam; **At randomization:** after baseline dental screening exam; **Two-weeks:** Two weeks after randomization; **Exit:** two weeks before end of school year dental exam

2. Caregiver self-efficacy and subjective norms will also be considered as potential **mediators** in the additional mediational analyses, and will be measured at the **Exit** in addition to **Baseline**.

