Analysis of Secondary Outcomes (Questionnaire data): Summary statistics (including means and standard errors) for questionnaire responses for both the IPQ-RD and behavioral intention items within the caregiver questionnaire will be calculated by site and intervention group. This will be done for the overall questionnaire (IPQ-RD and behavioral intention), for each of the five IPQ-RD cognitive constructs, and the two behavioral intention questions. Analyses will be done by site and overall (controlling for site). A summary measure approach, based on the mean questionnaire response, will be used to compare questionnaire outcomes across intervention groups, for the overall questionnaire and by construct. Specifically, for each construct (or overall) a linear regression model will be used with the mean response as the dependent variable, and intervention group

indicators and selected baseline (control) covariates as independent variables. Inferences (that is, p-values and confidence intervals) will be performed assuming summary measures are normally distributed. This assumption will be tested using the Shapiro-Wilk statistic and if violated a suitable transformation of the summary measure used or a nonparametric approach (e.g., using ranks of the summary measures) conducted.

In the event of missing questionnaire responses, we will first assess whether the data are missing completely at random (MCAR), that is, whether missingness for a given item is dependent only on participant baseline characteristics and not further on any other item responses. This will be done using a generalized estimating equations (GEE) approach, that is, by fitting a multivariate generalized linear (e.g., logistic regression) model to missing data indicators for each item, including as explanatory variables selected baseline covariates and other item responses, and testing for an effect of the latter.

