In addition to assessing the overall effects of the interventions, we will investigate the mechanisms (or paths) through which interventions impact dental care receipt. As represented in Figure 1, we hypothesize that a significant portion of the intervention effect will occur via a three-link path: intervention will affect caregiver illness representation which will in turn affect behavioral intention which will in turn affect dental care receipt. Initially, we will consider an overall average score for caregiver illness representation and for behavioral intention. We have previously developed a generalized causal mediation analysis methodology (Albert and Nelson, 2011) which we can use to estimate and test this specific path effect. It is possible that other paths may also be involved – namely, a direct path (possibly involving unidentified mediators) from intervention to dental care receipt, and paths through either caregiver illness representation or behavioral intention alone. We will therefore decompose the overall effect, and estimate the contribution of each of the four possible paths. For each (broadly defined) mediator, we may be interested in examining multiple components (e.g., summary scores or factors representing specific constructs for caregiver illness representation, and the two questions of behavioral intention). We may thus handle each mediator in our model as multidimensional (that is, a vector of latent or observed variables). In addition, we will consider a further refinement of the model, and decomposition of the intervention effect, by allowing separate paths through the individual components of each mediator. The 2-week measurement time for the mediators reflects the hypothesized time of maximum impact of the intervention. However, we will make use of the 7-month measurements of the mediators to assess any changes in the effect of the intervention over time, as well as the relationship between the mediators (at alternative times) and dental care receipt.

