14.2 Study Intervention and Study Questionnaires

Quality Assurance Procedures

The **Outreach Workers and study staff**, who will facilitate the receipt of intervention letters and access to the study questionnaires, will attend a 2-day in person training on the conduct of the study protocol and logistics (See MOP Section 5). In-class training will incorporate the topics of human subject protection, Good Clinical Practice (GCP), and the study protocol. A segment of the training will emphasize how data management procedures promote high-quality data collection and reduce threats to fidelity. Focus will be placed on following the procedures that have been outlined in the protocol, principles of data management, and forms administration procedures. All types of documentation will be discussed including forms filled out by participants and study forms completed by staff. For each, the purpose, instructions for completion and procedures to maintain accuracy will be addressed. As part of tracking and managing study records, staff members will learn how to document activities that occur with subjects, update study documentation, and use the tracking logs. As part of the training, the study staff will be certified in the topics presented to ensure their comprehension of the expectations.

Fidelity of the **Outreach Workers'** telephone contacts with caregivers will be assessed throughout the study to ensure that they have not provided additional information to the childrens' caregivers that might influence the outcome. (Refer to MOP Section 5).

For reliability purposes and to further assess the stability of the IPQ-RD presumably after visits to the dentists (between 2 and 4 weeks), we will randomly select a sub-sample of 60 caregivers (20 each in arms 1, 2, and 4) to respond to the IRQ-RD after 4 weeks.

Quality Control Procedures

The first ten (10) **Outreach Workers** telephone contacts (reminder calls to return the questionnaires) will be audio recorded in digital media and reviewed. Then, the first ten (10) of the following remaining type of call will be recorded and reviewed for each Outreach Worker (confirmation of receipt of referral letters-calls #2, and reminders to return completed questionnaires-calls #4 and #6). At the beginning of the study, the **Project Coordinators** will review the first ten telephone contacts to ensure fidelity of the calls and accuracy of data recording.

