APPENDIX C: IPQ-RD and Caregiver Questionnaire

In English:

- 1. Baseline IPQ-RD**
- 2. Baseline Caregiver Questionnaire**
- 3. 2-week Follow-up IPQ-RD**
- 4. 2-week Follow-up Caregiver Questionnaire**
- 5. Final Follow-up IPQ-RD**
- 6. Final Follow-up Caregiver Questionnaire**

In Spanish:

- 1. Baseline IPQ-RD**
- 2. Baseline Caregiver Questionnaire**
- 3. 2-week Follow-up IPQ-RD**
- 4. 2-week Follow-up Caregiver Questionnaire**
- 5. Final Follow-up IPQ-RD**
- 6. Final Follow-up Caregiver Questionnaire**

Site: _____ ID# _____

Family Access to Dentist Study

**Your Feelings
About Cavities**

January 29, 2015

Baseline IPQ-RD

Site: _____ ID# _____

Instructions:

We are interested in your views about your child's cavities (tooth decay). Please indicate how much you agree or disagree with the following statements about cavities by circling one of the following responses for each question: **strongly agree (1), agree (2), neither agree nor disagree (3), disagree (4), strongly disagree (5)**.

1. *Please tell us whether you believe each of the following is a symptom related to dental cavities in children:*

1a. Tooth pain	Yes	No
1b. Tooth sensitivity to hot or cold	Yes	No
1c. Hole in tooth	Yes	No
1d. Dark or white spot on tooth	Yes	No
1e. Swelling in face or gums (including a gum boil or abscess)	Yes	No

Please circle the number of the best answer for each question. If your child has not had cavities, please respond how you would if they did.

About your child:

Strongly Agree	Agree	Neither Agree nor Disagree	Disagree	Strongly Disagree
----------------	-------	----------------------------	----------	-------------------

2. Cavities in my child is a serious illness.	1	2	3	4	5
3. Cavities in my child has had a big effect on his/her life.	1	2	3	4	5
4. Cavities in my child has had a big effect on how he/she smiles.	1	2	3	4	5
5. Cavities in my child has had a big effect on his/her behavior at home.	1	2	3	4	5
6. Cavities in my child has had a big effect on his/her school work.	1	2	3	4	5
7. Cavities in my child has had a big effect on his/her self-worth.	1	2	3	4	5
8. Cavities in my child is disabling.	1	2	3	4	5

Site: _____ ID# _____

About you:	Strongly Agree	Agree	Neither Agree nor Disagree	Disagree	Strongly Disagree
	1	2	3	4	5
9. Cavities in my child has a big impact on my life.	1	2	3	4	5
10. I cannot easily live with my child's cavities.	1	2	3	4	5

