About you:	Strongly Agree	Agree	Neither Agree nor Disagree	Disagree	Strongly Disagree
	1	2	3	4	5
18. There is a lot I can do to control my child's cavity symptoms.	1	2	3	4	5
19. What I do decides if my child's cavities get better or worse.	1	2	3	4	5
20. There is a lot I can do to stop my child's cavities once they start.	1	2	3	4	5
21. There is a lot I can do to prevent cavities in my child.	1	2	3	4	5

Site: _____ ID#_____

About your child:

22. My child's cavities will not get better over time.

23. Cavities in my child are likely to be long-lasting rather than short-term.

Strongly Agree	Agree	Neither Agree nor Disagree	Disagree	Strongly Disagree
----------------	-------	----------------------------	----------	-------------------

1	2	3	4	5
1	2	3	4	5

About your child:

24. Cavities in my child may change from time to time.

25. There will be times when my child's cavity symptoms get worse and times when they get better.

Strongly Agree	Agree	Neither Agree nor Disagree	Disagree	Strongly Disagree
----------------	-------	----------------------------	----------	-------------------

1	2	3	4	5
1	2	3	4	5

About you:

26. I have a clear understanding of my child's cavities.

27. My child's cavity symptoms are not confusing to me.

Strongly Agree	Agree	Neither Agree nor Disagree	Disagree	Strongly Disagree
----------------	-------	----------------------------	----------	-------------------

1	2	3	4	5
1	2	3	4	5

About you:

28. I get really sad and upset when I think about my child suffering from cavities.

29. Seeing my child with cavities worries me.

30. Seeing my child with cavities makes me feel angry.

31. Seeing my child with cavities can make me feel helpless.

Strongly Agree	Agree	Neither Agree nor Disagree	Disagree	Strongly Disagree
----------------	-------	----------------------------	----------	-------------------

1	2	3	4	5
1	2	3	4	5
1	2	3	4	5
1	2	3	4	5

Site: _____ ID#: _____

32. Causes of children's cavities:

We would like to know what you think causes cavities in children. There is no correct answer. We are interested in your own ideas about children's cavities rather than what others (including doctors or family) may have told you. Below is a list of possible causes.

Please tell us how much you agree or disagree with each cause by circling the number that best fits your answer: **strongly agree (1), agree (2), neither agree nor disagree (3), disagree (4), strongly disagree (5).**

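### The secondary outcome is change in IPQ-RD, but the between-arm model in 12.4 fixes no time point, has no change term and does not name the baseline score as a covariate

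*Combined protocol and SAP*

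**What the plan says.** The Protocol Summary sets the secondary objective: "To assess changes in parent/caregiver illness representation/perception and behavioral intention between enrollment (beginning of school year), 2-week and 7-month follow-up". Section 3.2.2 repeats it at outcome level: "The change in IPQ-RD and behavioral intention scores will be calculated between baseline, two week, and final follow-up". No interval is named as the principal one. The footnote to Table 3.2.1 places baseline "prior to screening dental exam", the second questionnaire two weeks after randomization, and the exit questionnaire two weeks before the end-of-year exam.

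Under Analysis of Secondary Outcomes in 12.4, the model that compares arms is described in one sentence: "a linear regression model will be used with the mean response as the dependent variable", with arm indicators and unspecified baseline control variables on the right-hand side. The only covariate list in 12.4 belongs to the care-receipt model. It contains the child's age and race and the caregiver's socioeconomic status, education and marital status, and no questionnaire score.

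The mediation paragraph later in 12.4 does mention timing: "The 2-week measurement time for the mediators reflects the hypothesized time of maximum impact of the intervention". It adds that the 7-month scores will be used to see whether the intervention effect changes over time, but gives no model for this.

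Section 12.2 states 80% power per site for a 10-point difference in mean score (127 versus 117, SD 27). It gives no time point there either, and the SD is that of the score, not of its change.

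**The concern.** The objective and the outcome definition are about change, while the model is about an undated mean. A 2-week score, a 7-month score, a raw change score at either time and a baseline-adjusted score can all be defended from the text. The choice could therefore be made after the data are seen. These analyses also differ in precision, and the most efficient one depends on a covariate that the plan collects but does not name.

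The time points are not interchangeable. Baseline is answered before the school screening, the 2-week form shortly after the referral, and the exit form after months in which some children will have been treated. Section 12.2 expects receipt of care in 19%, 37% and 57% of the three main arms. A between-arm difference at exit may therefore include the effect of care received as well as the effect of the letter on perception.

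**Working it through.** **Inputs.** From 12.2: n = 102 per arm per site, difference 10 points, SD 27. The allocation in 5.4.1 agrees with the n: 330 × 17/55 = 102. Assumed: two-sided 0.05 (12.2 does not state it for this endpoint, but 12.4 uses 95% intervals), equal SD at each time, and a correlation r of 0.3 to 0.7 between baseline and follow-up. The documents give no r.

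**The plan's own figure.** Power = Φ(10 / [SD × √(2/n)] − 1.96).
- √(2/102) = 0.1400, so the standard error is 27 × 0.1400 = 3.78.
- 10/3.78 = 2.645, less 1.96 leaves 0.685, and Φ(0.685) = 75.3%.
- 80% needs n = 2 × (1.96 + 0.842)² × 27²/10² = 114.4, so 115 per arm.

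The stated 80% is not reproduced at 102. It is approached with 110 per arm (330/3, ignoring the two small arms), which gives 78.4%. A three-group F-test with assumed means of 127, 117 and 117 gives 78.2%.

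**The candidate analyses at 102 per arm.** Only the SD in the formula changes:
- follow-up score alone: 27
- adjusted for baseline: 27 × √(1 − r²)
- raw change: 27 × √(2 − 2r)

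| Assumed r | Follow-up alone | Baseline-adjusted (SD) | Raw change (SD) |
|---|---|---|---|
| 0.3 | 75.3% | 79.2% (25.8) | 60.9% (31.9) |
| 0.5 | 75.3% | 86.3% (23.4) | 75.3% (27.0) |
| 0.7 | 75.3% | 95.9% (19.3) | 92.7% (20.9) |

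Raw change is less precise than the follow-up score alone when r is below 0.5. The adjusted analysis is the most precise of the three at every r shown, and it reaches 80% at r of about 0.33.

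Adjustment also serves the change objective. In a linear model that contains the baseline score, the estimated arm difference is the same whether the dependent variable is the follow-up score or the change from baseline.

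**The case against.** Several points against the concern stand.

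- **Timing is not absent from 12.4.** The mediation paragraph names 2 weeks and 7 months, and IPQ-RD is one of those mediators. That paragraph does not fix the time point of the between-arm regression, and it does not bring baseline into it.
- **Not named is not excluded.** The unspecified baseline covariates could include the IPQ-RD score.
- **A separate analysis plan is listed** under Supplemental Materials, and 3.2.2 says change will be calculated. The finding is therefore that 12.4 leaves the analysis unspecified. A reader might conclude that the objective goes unanswered, but the data for IPQ-RD change are collected and the documents do not support that conclusion.
- **The mean is most naturally a mean over items**, because missing data are handled item by item. Averaging over time points is an unlikely reading, though the wording does not rule it out.
- **Randomization protects the 2-week contrast.** Learning the screening result happens in every arm, so it confounds within-arm change and not the between-arm comparison.

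A reader might also infer that the three questionnaires measure three distinct disease states, and that treatment pushes the exit score the wrong way in the arm where the letter works best. The second idea starts from items such as number 22 ("cavities will not get better over time"), where disagreement after treatment is reasonable yet raises the score, which 3.2.2 reads as worse. The documents do not establish either inference:

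- On the plan's rates, 43% to 81% of children in the main arms would still be without care at exit, so exit is a mixture and not a post-treatment state.
- All three forms carry the instruction "If your child has not had cavities, please respond how you would if they did", and nothing shows how many caregivers answer hypothetically.
- Items 3 to 7 and 12 are worded retrospectively, so treatment need not change the answer. Items 14, 15, 26 and 27 could move toward agreement after treatment, which lowers the score.
- No scoring key is shown.
- The 57% care rate includes caregivers who only had an appointment, and it belongs to the letter plus guide. The 10-point effect in 12.2 is for the CSM letter, whose expected care rate is 37%.

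The net direction of any exit shift is therefore unknown, and no size can be put on it.

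**Conclusion.** The finding holds as a gap in specification. The secondary outcome is change, and the 12.4 model that compares arms sets no time point, has no change term and does not name the baseline score. The gap matters for precision. Power at the planned 10 points per site is about 75% for a follow-up score alone, 79% to 96% with baseline adjustment, and 61% to 93% for raw change. These figures rest on two-sided 0.05, SD 27 at each time and r between 0.3 and 0.7, all taken at 102 analysed caregivers per arm. The mismatch with the stated 80% is a side result, and the finding does not depend on it.

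At exit, only a caution is justified: some caregivers will answer after their child has had care, at rates expected to differ by arm.

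Within-arm change from baseline should not be read as an effect of the letter. The screening result falls between the two measurements. In addition, the English item 32 asks about causes in the caregiver's own child at baseline and in children generally at both follow-ups.

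The primary outcome is not affected.

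**What to change.** In 12.4, under Analysis of Secondary Outcomes:

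1. Name the 2-week IPQ-RD score as the principal between-arm comparison, in line with the plan's own statement about the time of maximum impact.
2. Regress it on arm, site (in the overall model) and the planned covariates, plus the caregiver's own baseline IPQ-RD score. List those covariates.
3. Analyse the 7-month score in a separate model with the same baseline adjustment, so that the 7-month part of the objective is kept. Do not average it with the 2-week score. State that receipt of care may contribute to any arm difference, in an unknown direction.
4. State that within-arm change from the pre-screening baseline is descriptive and is not an effect of the letter.

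The cost is analysis-plan wording only, since all three questionnaires are already collected. The small downside is that one time point is given priority over the other.

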Arm 5 (N=204): The fifth arm (control) is the modified standard letter (based on November 2007 guidelines for Oral Health Screening in Ohio Schools). This letter is consistent with others used across the country and will be used in both the Ohio and Washington sites.

All letters will be sent home with the child on the day of the screening and mailed to the caregiver’s address within 24 hours. The address will be obtained during recruitment and verified with the school secretary.

A description of the recruitment, enrollment, randomization, and follow-up is below:

Caregivers will be recruited at the beginning of the school year and complete baseline forms (consent form, Illness Perception Questionnaire-Revised for Dental (IPQ-RD) questionnaire, and caregiver questionnaire) prior to dental screening and randomization (Figure 4.2.2). Children in K-4 whose parents have consented/assented will receive a screening exam in early October 2015. Caregivers whose children have no cavities or who have emergent needs will not participate further in the clinical trial. The baseline data from discontinued child and caregiver participants will be used only for baseline descriptive comparisons.

At the same time following screening exams eligible caregivers of children with restorative referrals will be randomized. Caregivers will be followed at 2 time points: 2 weeks after the receipt of the intervention letter and 2 weeks prior to the final (exit) study visit examinations in May 2016 (approximately 7 months after the initial dental exam). At both time points caregivers will complete the IPQ-RD and the caregiver questionnaire. A small sub-sample of 60 caregivers will be randomly

sampled from arms 1, 2 and 5 (20 per arm), to complete the IPQ-RD 1 month after enrollment for reliability purposes. All questionnaires will be mailed to the home address and asked to be returned to the class-room teacher or the outreach staff. Further, outreach staff will ensure that the caregivers received and returned the materials through follow-up calls. The schedule and scripts for the call are contained in the MOP (Table 6.1 and Appendix 6). Children will have a follow-up dental exam in May 2016.

[figure not shown]

Figure 4.2.2 Flowchart for Recruitment, Enrollment, and Randomization

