With regard to our secondary endpoint, the overall IPQ-RD score, we note that our expected sample size will provide for each site 80% power to detect an 10 point decrease in the mean score (e.g., from an expected mean of 127 for the standard letter to 117 for the CSM referral letter) assuming a common standard deviation of 27 (estimated from previous data). A decrease in IPQ-RD scores indicates better illness representation/perception of caregiver. Since the IPQ-RD has never been utilized previously, we refer to a popular rule of thumb (Cohen, 1988) which considers the above standardized effect size of 0.37 (10/27) as a medium, and thus plausible, effect size.

The statistical test of the effect of the targeted component (timeline) will involve a comparison of 408 (Arm 1, 2) versus 48 (Arm 3, 4) subjects. This test may have low power, particularly if the effect of the targeted text is not large. However, including these arms will allow this effect to be estimated and thus provide some idea of its relative contribution in this exploratory analysis, as well as allow us to detect a large effect (if the component is responsible for a large proportion of the CSM referral letter effect).

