If the MCAR assumption is deemed reasonable (no significant effect found), we will conduct the above regression analyses with mean outcomes based on available data. A weighted analysis (that is, regression with the use of the weighted least squares criterion) will be conducted to adjust for differential missingness (thus, non-homogeneous summary measure variances) among participants. If the MCAR assumption is found to be violated we will use a multiple imputation approach (in conjunction with the summary measure approach) using a suitable imputation model (i.e., using other item responses). For each construct (or overall) we will perform an F-test for a difference in the mean summary measure among the three intervention groups, and obtain nominal 95% confidence intervals for pairwise mean differences. If necessary, we will include a random effect for school.

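### If imputation is triggered, the questionnaire imputation model named in the plan leaves out study arm and the analysis covariates, which pulls arm differences toward zero; the size depends on what is missing

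*Combined protocol and SAP*

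**What the plan says.** All of this is in Section 12.4, under the analysis of secondary outcomes, unless another place is named.

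- **Analysis model.** For each IPQ-RD construct and overall, "a linear regression model will be used with the mean response as the dependent variable, and intervention group" indicators and selected baseline covariates enter as independent variables. The comparison itself is described as "we will perform an F-test for a difference in the mean summary measure among the three intervention groups", with pairwise 95% confidence intervals.
- **Missingness check.** The plan asks "whether missingness for a given item is dependent only on participant baseline characteristics and not further on any other item responses". Arm is not named in this check.
- **Two branches.** If the check finds nothing, available data are analysed by weighted least squares. Otherwise, "we will use a multiple imputation approach (in conjunction with the summary measure approach) using a suitable imputation model (i.e., using other item responses". No other predictor is named.
- **How forms arrive.** Section 4.2: "All questionnaires will be mailed to the home address and asked to be returned to the class-room teacher or the outreach staff". The IPQ-RD is collected at baseline (before randomisation), at 2 weeks and at exit.

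No rule is given for a form that does not come back, and no return rate is given anywhere.

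**The concern.** An imputation model should contain at least the variables in the analysis model. When the variable under test is left out, imputed values come from a distribution pooled over arms. They differ between arms only as far as the named predictors do. The estimated arm difference then mixes a true difference among observed values with a smaller, possibly zero, difference among imputed ones.

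At stake are the IPQ-RD and behavioral intention, which are the secondary outcomes and also the mediators in the planned path analysis. Constructs are analysed one by one, and behavioral intention has only two items. The design also expects a construct-specific effect, since Arms 3 and 4 differ from Arms 1 and 2 only by removal of the timeline content. Other items protect least in exactly these cases.

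**Working it through.** **Inputs from the documents.** Difference 10 points (127 vs 117), SD 27, 102 per main arm per site (Section 12.2). The IPQ-RD form has 41 five-point items (items 2–31 are 30; 32a–32k are 11). **Assumed, because the documents give nothing:** missing fractions, correlations between items and between waves, and two-sided 5% tests for the IPQ-RD.

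**1. The plan's own figure.** Section 12.2 says "our expected sample size will provide for each site 80% power to detect an 10 point decrease in the mean score". The standardised effect is 10/27 = 0.37, as stated. Power = Φ(10 / (27√(2/n)) − 1.96).
- n = 102: Φ(2.645 − 1.96) = 75.3%.
- n = 110 (330/3, ignoring the two small arms): 78.4%.
- 80% needs 2 × (1.96 + 0.842)² × (27/10)² = 114.4, so 115 per arm.

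The stated 80% is therefore not reached at 102 per arm. That is a separate matter; here 75.3% is only the no-missing-data reference.

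**2. Whole forms imputed from baseline, without arm.** Baseline precedes randomisation, so the predictor has no expected arm difference and the imputed values carry none. Expected estimate = (1 − m) × 10, which is 9.0, 8.0 and 7.0 at m = 10%, 20% and 30%. A simulation (102 per arm, 1500 replicates, 10 imputations, Rubin's rules, baseline-to-follow-up correlation 0.5, loss unrelated to arm) gives:

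| Missing | Without arm: estimate, power | With arm: estimate, power |
|---|---|---|
| 10% | 8.9, 64% | 9.9, 70% |
| 20% | 8.1, 48% | 10.1, 67% |
| 30% | 7.0, 34% | 10.1, 62% |

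Monte Carlo error of the mean estimate is about 27√(2/102)/√1500 = 0.1 point. Imputing from another follow-up wave would lose less than this if that wave carries part of the effect.

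**3. An effect in one construct score, missing as a block, other items observed.** Effect 0.37 SD, correlation 0.4 with the other items, 204 per arm. Closed form 0.37 × (1 − m): 0.333, 0.278 and 0.222 at 10%, 25% and 40%. Simulated without arm: 0.33, 0.27 and 0.22. With arm: 0.37, 0.36 and 0.38.

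**4. A two-item scale imputed only from its partner item.** Fraction kept ≈ (1 − m) + m(1 − m)r. At m = 20% and r = 0.5: 0.80 + 0.08 = 0.88.

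**5. Gaps within the long form, overall score.**
- Scattered items (5–20% missing, inter-item correlation 0.2–0.5): 97–100% of the difference is kept. This holds even when only seven of the 41 items shift, because the remaining items of that block still carry the effect.
- Half the items missing as a block, common shift: 0.218/0.227 = 0.96 when 25% of caregivers are affected, and 0.203/0.216 = 0.94 when 40% are. That is a loss of 4–6%.

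**The case against.** Several points on the other side are sound.

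- **The branch is conditional.** Imputation runs only if the check fails; otherwise available data are used. The simulations impose loss unrelated to arm in order to isolate the effect of omitting arm, and in that setting the plan would normally not impute. This stands: the bias is a consequence of one branch, not a certainty. The branch is a realistic prospect, though. On the 2-week and final caregiver forms, skip instructions make the intention items depend on the answer about a dental visit. That skip pattern is a separate problem, which adding arm would not fully cure.
- **Arm is not expressly excluded.** The omission is read from a short parenthetical and from silence. The supplemental materials list a separate SAP whose text is not available here; if it names arm, Section 12.4 needs only to be aligned. But the parenthetical is worded as a definition, not an example, and following it as written gives the shrinkage shown.
- **Unreturned forms.** A reader might infer that a caregiver who returns no form cannot be imputed at all. The documents do not support that: the named item responses are not limited to one form or wave, and a baseline form should exist. What is true is that the plan is silent. If only same-form items are meant, these caregivers drop out, and omitting arm cannot shrink scores that are never imputed. If other waves are meant, the loss in step 2 applies. The two harms are alternatives and should not be added.
- **Whole-form loss may be modest.** Reminder calls are planned at both follow-ups, and teacher help at 2 weeks. With no return rate given, neither a small nor a large loss can be claimed.

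**Conclusion.** The point holds as a conditional one. If the MCAR check fails and the imputation model is used as described, arm differences on the questionnaire outcomes are biased toward zero.

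The loss is negligible to small (about 0–6%) for scattered or half-form gaps in the overall IPQ-RD. It approaches the missing fraction for whole forms imputed from baseline, and for a construct missing as a block whose effect the other items do not carry. The two-item example falls between, at 12%. These sizes rest on assumed missing fractions and correlations.

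A reader might take the largest figures as a forecast for the trial; nothing in the documents supports that. The primary outcome comes from dental examination and is not touched, and the direction of bias would not create a false claim of benefit. This is a free improvement to the plan.

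**What to change.** In Section 12.4, replace the parenthetical on the imputation model with a list of predictors:

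- study arm, using the same indicators as the analysis model;
- site and the covariates of the analysis model;
- baseline and other-wave IPQ-RD and intention scores, alongside other items on the same form where available;
- the child's dental care outcome, because these scores are later related to it in the mediation analysis.

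State that construct scores of caregivers who return no form at a wave are imputed from this model. Arm should enter as a predictor. Imputing separately by arm is not workable with N=24 in each of Arms 3 and 4, about 330 × 2/55 = 12 per site, against 41 items.

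Cost: SAP wording and slightly more programming; no new data.
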